12.2.2 APOE Genotype and other DNA Markers

DNA will be extracted from participant blood samples at the baseline visit and will be analyzed for APOE genotype. This will allow secondary analyses of data on the impact of the APOE genotype on putative biomarkers of AD, clinical outcome measures, and adverse events. APOE polymorphisms are an important genetic risk factor for AD. Individuals with one or two Apolipoprotein epsilon 4 (APOE4) alleles have a higher risk of developing AD and an earlier age of onset. Furthermore, those with one or two APOE4 alleles exhibit a more rapid rate of clinical change in some, but not all studies.

Blood is collected in a uniform fashion using EDTA as anti-coagulant, as described in the Laboratory Manual. Participants will be asked to consent to optional DNA banking for future research studies.

12.2.3 Plasma for Biomarkers and Pharmacokinetics

Plasma samples will be collected at the baseline visit and during the confinement visit every hour for analysis of biomarkers, inflammatory factors, dopamine, acetylcholine and drug level analyses.

Biomarker and PK analyses sample collection will be performed on the 10 mL EDTA plastic tube whose collection is described in the Laboratory Manual.

12.2.4 Blood Samples for Exosomes

Blood will be collected in the morning, after an overnight fast, in EDTA tubes and will be subjected to two sequential centrifugations to generate platelet-poor plasma within one hour from the blood draw, as described in the Laboratory Manual. **Note** - for exosomes draws at the confinement visit after the 0-hour sample, strict fasting is no longer required. Low lipid foods (e.g., apple, banana, bread) are allowed.

13 PERSONNEL REQUIREMENTS

The site PI is responsible for the overall conduct of the study at the site. The PI is to supervise project personnel and ensure that clinical raters maintain a high level of skill and accuracy in conducting assessments. Additionally, the PI will perform or supervise clinical evaluation of all subjects and ensure protocol adherence. Additional key personnel will be required, as outlined in the procedure manual.

14 ADVERSE EVENTS (AEs)

14.1 Definition

An AE is defined as per the US Code of Federal Regulation, Title 21, Part 312.32 [<http://www.accessdata.fda.gov/scripts/cdrh/cfdocs/cfcfr/cfrsearch.cfm?fr=312.32>]. An AE is any untoward medical occurrence associated with the use of a drug in humans, whether or not considered drug related.

Collection of adverse events will begin once informed consent is signed and will continue until the follow-up phone call performed on the day after discharge. Adverse events include but are not limited to: (1) worsening or change in nature, severity, or frequency of conditions or symptoms present at the start of the study; (2) Subject deterioration due to primary illness; (3) intercurrent illness; and (4) drug interaction. An abnormal laboratory value will only be reported as an AE if the investigator considers it clinically significant, or if it leads to the Subject being withdrawn from the study.

The investigator should attempt to establish a diagnosis of the event based on signs, symptoms, and or other clinical information. In such cases, the diagnosis should be documented as the AE and not the individual signs or symptoms. Symptoms and conditions present at the beginning of the study will be characterized, so that AEs can be defined as any new symptom, or any increase in frequency or severity of an existing symptom. Adverse events should be described with medical terminology so that the event can be matched against a medical coding dictionary, such as MedDRA (Medical Dictionary for Regulatory Activities).

Investigators should report their assessment of the potential relatedness of each AE to the protocol procedure, and to the investigational product, and/or drug delivery system used in the protocol.

Following questioning and evaluation, all AEs, whether determined to be related or unrelated to the study drug by a medically qualified site PI or clinician must be documented in the Subject's records, in accordance with the investigator's normal clinical practice, and on the AE electronic case report form (eCRF).

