Because a substantial proportion of the adverse events observed in AD patients treated with cholinesterase inhibitors appear to reflect the cholinomimetic properties of molecules in this class, Posiphen’s highest tolerated dose is determined by the levels of the N1-norposiphen in blood and brain.

While the $t_{1/2}$ of Posiphen in plasma was 5 hours as seen in the SAD and MAD studies, the $t_{1/2}$ in CSF/brain was longer than 12 hours. Concentrations of Posiphen in the brain, extrapolated from blood and CSF, were 8 times higher than in plasma. 10 days of treatment with Posiphen normalized CSF levels of sAPP, tau, α SYN and a series of inflammatory markers. The concentration and persistence of Posiphen in the brain suggest that much lower doses of drug administered once daily could achieve the desired pharmacological effect.

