Outcome measures to assess pharmacodynamics: Translational inhibition of the aSYN mRNA will result in decreased production of aSYN, which may be reflected by decreased secretion of the aSYN monomers and oligomers into the spinal fluid. Similarly, translational inhibition of the APP mRNA will result in decreased production of APP and its fragments, which may be reflected by decreased secretion of the A β monomers and oligomers into the spinal fluid. We also will measure secreted sAPP α and sAPP β and levels of tau and p-tau in CSF. sAPP reflects processing of APP by α -secretase to produce sAPP α and β -secretase (BACE) to produce sAPP β . Tau levels are being measured since we found that tau translation may be under the regulation of a similar iron-responsible element (IRE) that may also be affected by Posiphen treatment. In fact, we have measured in human CSF and in mouse brain that tau and p-tau levels are lowered by Posiphen treatment.

Safety outcome measures: Reports of adverse events (AEs) and serious adverse events (SAEs) during exposure to Posiphen will be collected to evaluate if there are any significant clinical safety issues for the study population. All SAEs occurring up to 30 days after last study drug administration that are considered drug-related must also be reported. Extensive clinical and laboratory safety data already exist for Posiphen; therefore, this approach will be sufficient in the proposed study.

Clinical, functional and cognitive assessment measures: Although clinical benefit is unlikely due to the short duration of this study, AD and PD specific tests will be performed. It is predicted that cognition and function will remain stable over the course of drug exposure; however, this will be assessed formally in the clinic. For both populations, the MMSE ([Folstein 1975](#)) will be administered as a global measure of cognition and the Coding subtest from the Weschler Adult Intelligence Scales, 4th edition (WAIS-IV) will serve as a sensitive measure of CNS dysfunction. The subjects with AD will also be administered the ADAS-Cog 14 ([Schafer 2012](#)). The subjects with PD will be administered the [Hoehn & Yahr \(1967\)](#) for determination of inclusion into the study. Functional impairment will be evaluated using the Clinical Dementia Rating (CDR) scale ([Berg1988](#)) for AD and the MDS-UPDRS ([Goetz 2008](#)) for those with PD.

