5.3 Risk/Benefit Associated with CSF Sampling

The most frequent adverse event associated with these studies was post-lumbar puncture headache. This was successfully managed by blood patching if a participant is unresponsive to orally administered fluids and/or caffeine.

Other potential risks include meningitis, pain or tingling sensation in the lower extremities, temporary eye weakness or double vision, infection or bleeding at the site of catheter insertion,

pain at the site of insertion, backache, epidural or subdural bleeding, infection, paralysis and potential injury to the nerve root.

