9.4.3 Post-Confinement 24-Hour Phone Follow-up

Approximately 24 hours following discharge from the Confinement Visit the subject or a person designated to speak for them will be contacted by phone to confirm the subject's well-being and to query about any new AEs.

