15.2 Reporting SAEs

Collection of serious adverse events will begin once informed consent is signed (regardless of study drug exposure) and will continue until 30 days following the last dose of study drug. All SAEs must be reported to the Medical Monitor, the Sponsor, Project Directors and the Coordinating Center within 24 hours of learning of the event. This in turn will trigger an alert to

the appropriate Coordinating Center personnel and Protocol Project Directors, which will lead to the initiation of the creation of the report. A notification will be sent to all participating sites and the DSMB once the report is available. Sites will inform their IRB of the event based on local IRB requirements. The Sponsor is the IND holder and is responsible for submitting any SAEs according to the FDA reporting requirements.

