23 APPENDIX 1: SCHEDULE OF EVENTS

Visit Timing ^a	Day -42 to 0		Day 14 (± 4)	1-3 days prior to confinement	Days 25 (± 2)		
Procedures	Screening	Baseline	Phone	Pre- Confinement Phone Contact	Confinement		
					Admission	6-Hour Sampling	Discharge ^e
Informed Consent	X						
Demographics	X						
Medical and Psychiatric History	X						
Height and BMI	X						
Inclusion and Exclusion Criteria	X	X					
Urine Dipstick Pregnancy Test	X						
Physical and Neurological Examination	X	X			X		X
AD & PD: MMSE	X	X			X		
AD: CDR	X	X			X		
AD: ADAS-Cog 14		X			X		
AD & PD: WAIS-IV		X			X		
PD: MDS-UPDRS	X ^g	X			X		
C-SSRS	X	X			X		
Vital Signs ^b	X	X			X	X	X
Clinical Lab Safety Tests	X	X ⁱ			X ⁱ		
12-Lead ECG	X	X			X		X
MRI of Brain ^c	X						
Adverse Events	X	X	X	X	X	X	X
Prior/Concomitant Medication	X	X	X	X	X	X	X
Randomization		X					
Dispense Study Drug		X					

Dosing Study Drug in Clinic		X				X	
Study Drug Compliance Check			X	X	X		
APOE Genotype and DNA Markers		X					
Blood Sampling for PK		X				X	
Lumbar Puncture for baseline Pharmacodynamics		X					
LP Catheter Placement ^h					X		
Sampling for Biomarkers in Blood, Plasma and CSF		X				X ^f	
24-Hour Phone Follow-Up ^d		X					X
Lumbar Xray ^h (Optional)	X						

^a Refer to Section 9 for more details on visit timing and windows.

^b Vital signs will include sitting blood pressure, pulse, temperature, respiration rate, and weight, except during the 6-hour Sampling Phase of the Confinement Visit when weight will not be included.

^c An MRI of the brain will only be conducted if there is no brain MRI available from within the window specified in Inclusion Criteria.

^d Phone Follow-up should occur approximately 24-hours after completion of the LP procedure at Baseline and after discharge from the Confinement Visit.

^e The Early Discontinuation Visit will contain the same assessments as the Pre-confinement Visit.

^f Sampling Times: 0,1,2,3,4,5,6 hrs (± 10 mins for collection)

^g Hoehn & Yahr Stage only for inclusion determination

^h X-Ray is only required if LP insertion will not be performed with fluoroscopy

ⁱ Safety labs at baseline and confinement (for sample 0 hour) should be taken fasted

24

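### SAEs are collected for 30 days after the last dose, but the last scheduled contact is a call about 24 hours after discharge, so later events are not actively solicited and new non-serious AEs fall outside collection

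*Protocol*

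**What the plan says.** Two collection windows are defined. For AEs, Protocol 14.1 starts at consent and "will continue until the follow-up phone call performed on the day after discharge". For SAEs, Protocol 15.2 starts at consent and "will continue until 30 days following the last dose of study drug", with no condition on causality. Protocol 4.2 words the SAE rule differently: "All SAEs occurring up to 30 days after last study drug administration that are considered drug-related must also be reported".

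The last scheduled contact is in Protocol 9.4.3: "Approximately 24 hours following discharge from the Confinement Visit the subject or a person designated to speak for them will be contacted by phone". Protocol 12.2.1 repeats it, and a footnote to Appendix 1 reads "Phone Follow-up should occur approximately 24-hours after completion of the LP procedure at Baseline and after discharge from the Confinement Visit". SAP Table 2 (SAP 5.1) carries the same schedule and ends at the same point.

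Protocol 14.2 requires that patients who already have an AE be followed until it resolves or stabilises. Protocol 15.2 starts the SAE reporting clock when the site learns of the event. SAP 5.3 defines a treatment-emergent AE by its start, on or after the first dose, and gives no end.

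On the Day 25 procedure, Protocol 5.3 calls post-lumbar-puncture headache the most frequent event and continues: "Other potential risks include meningitis, pain or tingling sensation in the lower extremities". The same list includes infection, epidural or subdural bleeding and nerve-root injury.

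**The concern.** Safety and tolerability are a primary outcome. The most invasive procedure in the trial, an indwelling CSF catheter with seven collections of up to 6 mL each, falls on the last day of treatment. Follow-up by scheduled contact then stops about a day after discharge. By contrast, the baseline lumbar puncture is followed by its own 24-hour call, the Day 14 call, the pre-confinement call and the confinement admission.

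The protocol sets a 30-day SAE window but schedules nothing in it after the first day or two. An SAE that starts later is recorded only if somebody tells the site. A new non-serious AE that starts after the call, such as back pain or a late headache, is not recorded at all. Counts of SAEs and of AEs related to a study procedure, both of which SAP 7.3.1 tabulates, could therefore be too low. A reader would have no means of telling how far.

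**Working it through.** There is no figure in the plan to reproduce. The check sets the timings side by side.

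**Inputs**
- Last dose: given after the hour 0 sample on the confinement day (Protocol 9.4.2); taken here as hour 0.
- Sampling: 6 h, then catheter removal (Protocol 9.4.2).
- Observation: at least 1 h after removal (Protocol 9.4.2).
- Call: about 24 h after discharge (Protocol 9.4.3).
- SAE window: 30 days = 720 h after the last dose (Protocol 15.2).
- Half-lives: 5 h in plasma; in the CNS, "in CSF/brain was longer than 12 hours" (Protocol 3.2; also 4.2).

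**Timing of the last contact, minimum stay**
- From last dose: 6 + 1 + 24 = 31 h, or 31/24 = 1.3 days.
- From catheter removal: 1 + 24 = 25 h.
- Window with no scheduled contact: 30 − 1.3 = 28.7 days; (720 − 31)/720 = 0.957, about 96%.

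**If the patient stays overnight** (assumption: discharge 24 h after the dose)
- From last dose: 24 + 24 = 48 h.
- Window with no scheduled contact: 28.0 days; (720 − 48)/720 = 0.933, about 93%.

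**Drug remaining at 31 h**, as 0.5^(t / half-life)
- Plasma: 31/5 = 6.2 half-lives; 0.5^6.2 = 0.014, about 1.4%.
- CNS at exactly 12 h: 31/12 = 2.58 half-lives; 0.5^2.58 = 0.167, about 17%, and more if the half-life is longer.

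**What happens to an event by type and onset**

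| Event | Treatment under the plan |
|---|---|
| AE open at the call | Followed to resolution or stability (14.2) |
| New non-serious AE after the call | Outside collection (14.1) |
| SAE after the call, to day 30 | Reportable under 15.2 if the site learns of it; no scheduled question |
| The same SAE, judged not drug-related | Reportable under 15.2; not within the 30-day rule of 4.2 |

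The last row is a direct conflict, and a catheter complication is the likely case: an SAE caused by the procedure need not be considered drug-related.

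**Database lock.** SAP 3.3 releases a cohort's randomisation schedule once its patients have completed the required schedule and the data are locked. Since that schedule ends at the 24-hour call, nothing stated prevents a cohort from being locked and unblinded while its last patients are still inside the 30-day SAE window.

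**The case against.** Different windows for AEs and SAEs are explicit in the protocol and are not in themselves a contradiction. The gravest catheter risks, such as meningitis or a subdural bleed, would ordinarily meet the SAE definition in Protocol 15.1 and so stay inside the 30-day window. Open AEs are followed. Drug exposure is observed over about 25 days of dosing with several contacts. Protocol 4.2 attributes cholinergic events mostly to peak concentration, and at the call only about 1.4% of plasma drug remains. The consent pages were not available for this review, and the protocol refers to a procedures manual, Coordinating Center SOPs and a DSMB charter. Patients may be told to report later events.

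Much of this stands, and it rules out several stronger readings:
- A reader might infer that late events go unascertained. For SAEs that is too strong: they are reportable but not actively solicited.
- A reader might infer that a 30-day SAE rate will be misreported. SAP 7.3.1.2 tabulates SAEs by system organ class and preferred term and defines no such rate.
- A reader might infer that a comparison of events after the baseline puncture with events after the catheter is spoiled. None is planned.
- A reader might infer bias between arms. All arms share the same post-dose schedule, so the truncation is the same in each by design.
- A reader might rest the point on drug carry-over. The 17% CNS figure gives it some support, but the plasma figure makes it the weaker argument.

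The schedule gap itself is not answered. Following known AEs does not find new ones, and a reporting clock that starts on learning of an event does not find it either. Spontaneous report is a doubtful sole method in a trial that admits patients with an MMSE of 18.

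**Conclusion.** The point holds in a bounded form. The protocol sets a 30-day SAE window and, in the documents available, schedules no contact for about 96% of it (93% if the patient is assumed to stay overnight). All 68 planned patients are affected (14 + 14 + 40). New non-serious AEs after the call are excluded by rule; late SAEs depend on unsolicited report. The case rests mainly on the Day 25 catheter procedure and the risks that Protocol 5.3 names.

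The consequence is possible under-counting in absolute safety tables. The documents give no onset times or rates for catheter events, so the number missed cannot be estimated. No sample size or power figure changes. The conclusion assumes that no unseen manual adds a later contact; if one does, it should appear in Appendix 1.

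Separately, the SAE rules in Protocol 4.2 and 15.2 conflict and must be reconciled in any case.

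**What to change.** 1. Add one scheduled telephone contact at 30 days after the last dose to Protocol Appendix 1, Protocol 9.4 and SAP Table 2. It should ask about SAEs and about any new event since discharge related to the catheter procedure or study drug.
2. Amend Protocol 14.1 so that those events are recorded. Extending collection of all non-serious AEs to 30 days is more debatable and is not needed to close this gap.
3. Reconcile Protocol 4.2 with 15.2 on whether the 30-day rule covers all SAEs or only drug-related ones.
4. State an end to the treatment-emergent window in SAP 5.3, and tabulate events with onset after discharge separately. Otherwise every late off-drug event recorded would count as treatment-emergent.
5. Make each cohort's safety lock wait for the 30-day contact.

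The cost is about 68 calls, with no added visit or procedure, and a safety lock up to 30 days later, which the existing SAE window already implies. The limitation is recall: a call at one month will find serious events better than transient ones such as a headache that has passed.

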14.2 Following Up on AEs

The investigator is obliged to follow subjects with AEs until the events have subsided, the conditions are considered medically stable, or the subjects are no longer available for follow up. Subjects who discontinue due to adverse experiences will be treated and followed according to established medical practice. All pertinent information will be entered into the eCRF. Adverse events will be reported to the Medical Monitor, Sponsor, and DSMB, per Coordinating Center SOPs and the DSMB Charter.

Because of the potential of additive cholinergic adverse events caused by a combination of Posiphen and cholinesterase inhibitors in some subjects, the severity of such adverse events should be carefully evaluated taking the criteria in [Appendix 2](#) into consideration (modified from CTCAE version 4.03.)

15 SERIOUS ADVERSE EVENTS (SAE)

15.1 Definition

A SAE is defined as per the US Code of Federal Regulation, Title 21, Part 312.32 [<http://www.accessdata.fda.gov/scripts/cdrh/cfdocs/cfcfr/cfrsearch.cfm?fr=312.32>].

An adverse event or suspected adverse reaction is considered "serious" if, in the view of either the investigator or Sponsor, it results in any of the following outcomes: Death, a life-threatening adverse event, inpatient hospitalization or prolongation of existing hospitalization, a persistent or significant incapacity or substantial disruption of the ability to conduct normal life functions, or a congenital anomaly/birth defect. Important medical events that may not result in death, be life-threatening, or require hospitalization may be considered serious when, based upon appropriate medical judgment, they may jeopardize the Subject and may require medical or surgical intervention to prevent one of the outcomes listed in this definition. Examples of such medical events include allergic bronchospasm requiring intensive treatment in an emergency room or at home, blood dyscrasias or convulsions that do not result in inpatient hospitalization, or the development of drug dependency or drug abuse.

15.2 Reporting SAEs

Collection of serious adverse events will begin once informed consent is signed (regardless of study drug exposure) and will continue until 30 days following the last dose of study drug. All SAEs must be reported to the Medical Monitor, the Sponsor, Project Directors and the Coordinating Center within 24 hours of learning of the event. This in turn will trigger an alert to

the appropriate Coordinating Center personnel and Protocol Project Directors, which will lead to the initiation of the creation of the report. A notification will be sent to all participating sites and the DSMB once the report is available. Sites will inform their IRB of the event based on local IRB requirements. The Sponsor is the IND holder and is responsible for submitting any SAEs according to the FDA reporting requirements.

16 DATA AND SAFETY MONITORING BOARD (DSMB)

A DSMB will review the safety information from the study on an ongoing basis. The DSMB, will identify the study-specific data parameters and format of the information to be reported, as well as the timing of reports based on the enrollment status of the study. The DSMB will initially be provided with data blinded to treatment status, but they may request unblinded data if there is a safety concern.

Additionally, the DSMB will be informed of the occurrence of any serious adverse events within 7 days of being reported to the Coordinating Center. The DSMB may at any time request additional information from the Coordinating Center.

Based on the review of safety data, the DSMB will make recommendations regarding the conduct of the study. These may include amending safety monitoring procedures, modifying the protocol or consent, terminating the study or continuing the study as designed. Using the Safety Review Process (review of lab data, vitals, and adverse events) and the DSMB, there is substantial oversight and case review to alert the investigators, in a timely manner, to any safety issues that may arise. Further details will be provided in the DSMB charter.

